Study Title “IVIg for Small Fiber Neuropathy With Autoantibodies to TS-
HDS and FGFR3”

NCT number: NCT03401073

Document Date: 11/29/2022

Protocol:

Study Design: This was a prospective 6-month double-blind placebo-controlled pilot study of IVIG for treatment of suspected immune mediated SFN associated with TS-HDS or FGFR-3. The trial was registered with ClinicalTrials.gov (NCT03401073).

Subjects: Potential research subjects were recruited from the panel of patients seen by neuromuscular/peripheral nerve groups at Beth Israel Deaconess Medical Center (BIDMC) (Boston, MA) and HonorHealth Neurology (Phoenix, AZ) and by patients seen at neighboring institutions in the Boston and Phoenix areas. Additional referrals were obtained through ClinicalTrials.gov. All recruited subjects provided signed informed consent as approved by the Institutional Review Boards of BIDMC and HonorHealth.

Inclusion Criteria: Patients were potentially eligible if they had clinically evident SFN in a length dependent or non-length dependent pattern as confirmed by history of symptoms that included burning, shooting, or prickling pain or dysesthesia for at least 6 months and examination findings demonstrating loss of pain sensation and/or loss of temperature detection in the distribution of pain. Subjects also required evidence of reduced intra-epidermal nerve fiber density (IENFD) seen on skin biopsy in the region corresponding to examination abnormalities, based on age and sex-matched normative values, using PGP 9.5 as the immunostain.¹⁵ Subjects required a baseline daily pain score on a visual analogue scale (VAS) of greater than or equal to 4/10. Patients also required elevated titers of autoantibodies to TS-HDS or FGFR-3 as measured by the Neuromuscular Clinical Laboratory at Washington University in St Louis using standard enzyme linked immunoassay (ELISA) assays as previously published.^{14,16} Antibody titers were measured at the time of screening and abnormal values measured at the Washington University laboratory within the 6 months prior to screening were accepted. Normative values are <10,000 for TS-HDS and <3,000 for FGFR3.

Exclusion Criteria: Individuals were excluded if they had evidence of large fiber neuropathy such as abnormal nerve conduction studies, motor weakness, absent vibration, proprioception or deep tendon reflexes. Individuals were also excluded if they were found to have other known causes for small fiber neuropathy: diabetes, prediabetes, HIV, Sjogren's syndrome, vitamin deficiency, toxin exposure, or monoclonal gammopathy. Patients were also excluded for generalized, severe musculoskeletal conditions other than SFN that would have prevented accurate assessment by the physician, or for an underlying condition that would put them at risk of complication from a biopsy such as anticoagulant use.

or high risk of infection. Other exclusions were a contraindication to IVIG because of renal dysfunction with creatinine >1.5 mg/dl, prior thrombotic event or a hypersensitivity reaction to IVIG in the past.

Screening: Study subjects underwent a detailed history, physical examination, laboratory studies, pain VAS scores, the Short-Form 36 question health survey (SF-36), antibody measurement of TS-HDS and FGFR-3 and skin biopsy evaluation of nerve fiber density at the distal leg and proximal thigh using standard methodology.

Randomization and Blinding: Subjects who were eligible for study inclusion were block randomized into 2 groups (IVIG or placebo) by a blinded statistician. All study personnel, study subjects and support staff were blinded to treatment assignment. Only the single research pharmacist who mixed the IVIG/placebo was aware of the treatment assignment and was not in communication with any study staff. IVIG and placebo were placed in opaque infusion bags that covered the entire treatment product and infusion line to prevent unblinding.

Study Medication and Treatment Allocation: Subjects received either IVIG or placebo. IVIG treatment involved an initial dose of 1 gm/kg (Gamunex, Grifols, Los Angeles, CA) daily for 2 days followed by 1 gm/kg in a single dose every 3 weeks for 21 weeks (for a total of 8 doses) with a maximum of 80 gm IVIG infusion. Normal saline was used as placebo and included in a volume equivalent to that of IVIG.

Study Procedures: The outline of the study protocol is seen in Supplemental Figure 1. At all study visits participants underwent review of inclusion and exclusion criteria, medical history, medication review, adverse effect review, and pain VAS scores (0-10 scale – reported as pain on the day of visit). At the screening and final study visits all subjects also completed skin biopsies at the distal leg,¹⁷ the Utah Early Neuropathy Scale (UENS),¹⁸ and the SF-36.¹⁹

Physical Examination: Detailed neurologic examinations were performed at baseline and at the final visit. The physical examination was quantified via the UENS.¹⁸ In brief, the UENS is a 42-point system that grades neuropathy from 0 (no neuropathy) to 42 (absent ankle reflexes, weakness at the toes, absent sensation to multiple modalities in the legs).

Pain Scores: Subjects rated their pain on an 11-point visual analogue Likert scale at every visit (where 0 = no pain and 10 = maximal pain). The location, exacerbating factors and character of pain were recorded at each visit. Subjects were treated with medications to reduce neuropathic pain at the discretion of the treating physician, including anti-convulsants, anti-depressants and opioids, typically in combination. Pain scores were measured while on medication. Subjects

were asked not to change doses of daily neuropathy pain medications while participating in the clinical trial. Subject use of pain medications was monitored at each study visit.

Skin Biopsy Evaluation of Intra-Epidermal Nerve Fiber Density (IENFD): All study participants underwent 3-mm punch skin biopsies 10 cm above the lateral malleolus at their baseline visit. Follow-up biopsies were taken 21-25 weeks later on the same leg adjacent to the original biopsy sites using standard techniques. Specimens were fixed and stained with PGP 9.5 (ubiquitin hydrolase, Chemicon).²⁰ All patients underwent IENFD counting by a blinded physician and results were expressed as a linear density for IENFD (number of fibers per millimeter).²¹

Statistical Analysis Plan:

Primary Outcome: The primary efficacy endpoint for this study was the change in IENFD between visits 1 and 8. We defined a clinically relevant change in disease endpoint as a >2.0 fiber/millimeter increase in IENFD between screening and final visit. We anticipated no change in IENFD between visits 1 and 8 in the placebo treatment arm. The change in IENFD was based on prior studies of lifestyle modification in diabetic neuropathy where increases in IENFD of >2 fibers/mm over 1 year were seen in 25% of patients associated with an improvement in neuropathic pain.²² Pain was not selected as a primary outcome measure because a separate ongoing clinical trial using IVIG in small fiber neuropathy was already investigating pain as an endpoint,² and also because of our specific interest was in evaluating IVIG for potential impact on disease modification.

Secondary Outcomes: Two secondary outcome measures are included in this study:

- 1) The change in neuropathic pain severity between visits 1 and 8.

We expected that individuals with immune mediated small fiber neuropathy treated with IVIG would have a >2-point reduction in neuropathic pain VAS score between screening and final visit. We anticipated a <1.5-point reduction in neuropathic pain VAS score between screening and final visit in the placebo group.

- 2) The change in quantified UENS scores, between screening and final visit.

We expected that individuals with immune mediated SFN treated with IVIG would have a >1 point reduction in the UENS score between screening and final visit. We expected that the placebo treated group would have no change in UENS score between screening and final visits.

Exploratory Outcomes: Safety in response to IVIG infusion and changes in distribution or character of pain associated with SFN in patients treated with IVIG.

This pilot study was being conducted in order to obtain adequate preliminary data for a larger clinical trial but was powered to answer the primary endpoint analysis. Secondary endpoints and exploratory endpoints are not included in the power analysis. The sample size of 10 participants per group was determined with an assumed change in IENFD rate of 0 fibers/millimeter in the placebo group and >2.0 fibers/millimeter in the IVIG group, a 1-sided α of 5%, and 80% power between the 2 groups, including the assumption of a dropout rate of 10% (2 patients). Therefore, the aim was to include in total 20 patients in the study.

The results were analyzed according to the intention-to-treat (ITT) protocol. For the primary ITT analysis, missing values were imputed as no change from baseline. Participants were analyzed for efficacy according to randomized treatment. For the SF-36 Health Survey, biopsy results, and UENS examination findings, the difference between baseline (screening period) and the end of the final visit was calculated. For the primary outcome measure, the proportion of patients with a decrease of at least 2.0 fibers/millimeter was compared between the IVIG and placebo groups with a χ^2 test, with mean and standard deviations reported. For secondary outcome measure, mean change in values between groups was compared using a student's T-test (2 tailed, 2 sample, homoscedastic variance). For pain VAS scores, ANOVA was used to measure differences in pain scores between IVIG and placebo groups.

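### The primary IENFD comparison ignores the baseline IENFD measured in every patient, so with 10 per arm a chance baseline difference carries into the result and precision is lost

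*Combined protocol and SAP*

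**What the plan says.** The Primary Outcome section of the SAP defines the endpoint: "The primary efficacy endpoint for this study was the change in IENFD between visits 1 and 8". The closing analysis paragraph says that for the biopsy results "the difference between baseline (screening period) and the end of the final visit was calculated", and gives the test: "the proportion of patients with a decrease of at least 2.0 fibers/millimeter was compared between the IVIG and placebo groups with a χ^2 test". Group means and SDs are to be given as well. No covariate, ANCOVA or other baseline-adjusted model appears anywhere in the document.

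The baseline value is available. The protocol section on skin biopsy says: "All study participants underwent 3-mm punch skin biopsies 10 cm above the lateral malleolus at their baseline visit". Randomization and Blinding says only that eligible subjects were "block randomized into 2 groups (IVIG or placebo) by a blinded statistician"; it mentions no stratification by baseline density.

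On size, the SAP says: "The sample size of 10 participants per group was determined with an assumed change in IENFD rate of 0 fibers/millimeter in the placebo group", against ">2.0 fibers/millimeter in the IVIG group", at a one-sided 5% level with 80% power and 10% dropout. It gives no SD of IENFD change and no correlation between baseline and final IENFD.

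**The concern.** Subtracting baseline is not the same as adjusting for it. If the slope of final on baseline IENFD is below 1, change is negatively related to baseline: patients who start low tend to gain more than patients who start high, in either arm. When the arms differ at baseline by chance, part of that difference appears in the contrast of raw change. The chi-square inherits the problem because its cut is applied to the same raw change.

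At stake is how far the primary result depends on which arm happened to start lower, in a small trial that is also meant to supply preliminary data for a larger one. The precision available from a measurement already taken is also left unused.

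**Working it through.** **Inputs from the SAP.** Difference 2.0 fibers/mm (0 against 2.0), one-sided 5%, 80% power, 10 per arm, 10% dropout.

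**Assumed, not in the documents.** Normal data; equal variances at baseline and final visit; correlation r between the two of 0.3, 0.5 or 0.7; no missing values; a directional chi-square at the one-sided 5% level. The cut is taken as an increase of more than 2.0, as Primary Outcome defines benefit. The analysis paragraph speaks of a decrease; that wording must be reconciled separately, and this point does not depend on it.

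**1. The plan's own figure.** The dropout step is consistent: 9/(1 - 0.10) = 10 per arm. The sample size itself cannot be reproduced, because no SD and no pair of response rates is given. Solving a one-sided 5% two-sample t-test with 80% power and difference 2.0 for the SD of change gives 1.63 (9 per arm) or 1.73 (10 per arm). Both are used below.

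**2. Precision.** With equal variances, the SD at each visit is SDc/√(2(1 - r)), where SDc is the SD of change. The error variance after ANCOVA, relative to raw change, is 1 - (1 - r)²/(2(1 - r)) = (1 + r)/2.

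**3. Carry-over.** A between-arm baseline difference D shifts the raw-change contrast by (1 - r)D in size. One standard error (SE) of D is SD × √(2/n). For 10 per arm and SDc = 1.73:

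- r = 0.3: SD = 1.73/√1.4 = 1.46; SE = 1.46 × √0.2 = 0.65; shift = 0.7 × 0.65 = 0.46
- r = 0.5: SD = 1.73/√1.0 = 1.73; SE = 0.77; shift = 0.5 × 0.77 = 0.39
- r = 0.7: SD = 1.73/√0.6 = 2.23; SE = 1.00; shift = 0.3 × 1.00 = 0.30

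The shifts are 0.30/2.0 = 15% to 0.46/2.0 = 23% of the planned effect. An imbalance of more than 1 SE in a given direction occurs in about 16% of trials.

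**4. Power at a true effect of 2.0** (simulation, 40,000 trials per setting):

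| | r = 0.3 | r = 0.5 | r = 0.7 |
|---|---|---|---|
| Variance ratio (1 + r)/2 | 0.65 | 0.75 | 0.85 |
| Raw-change t-test | 80% | 80% | 80% |
| ANCOVA | 91% | 87% | 83% |

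**5. The planned chi-square.** The chance of exceeding +2.0 is 50% with IVIG when its mean change is 2.0. With placebo it is 1 - Φ(2/1.63) = 11% to 1 - Φ(2/1.73) = 12%. Simulated over both arm sizes and the three values of r:

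| | All trials | IVIG starts >1 SE lower | IVIG starts >1 SE higher |
|---|---|---|---|
| Power, true effect 2.0 | 56-60% | 73-83% | 30-43% |
| False positives, no effect | 2-3% | 5-9% | not used here |

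**6. Sensitivity.** At r = 0.9 the precision gain is gone: ANCOVA 79% against 80% for the raw-change t-test, once the lost degree of freedom is counted. If the baseline SD were half the equal-variance value, with slope b and SDc unchanged, the variance ratio would be 1 - (1 - b)/8. That is 0.91 at b = 0.3 and 0.96 at b = 0.7. The 1-SE shift would halve, to 0.46/2 = 0.23 and 0.30/2 = 0.15 fibers/mm.

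**The case against.** The strongest reply is that an unadjusted comparison of randomised arms is valid, and that this is a self-described pilot. That stands: averaged over randomisations, the raw-change t-test holds its 5% level and the chi-square is conservative at 2-3%. What remains is dependence on the imbalance that actually occurs, and efficiency.

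A reader might infer that the trial is prone to false positives whenever IVIG starts lower. For a t-test on mean change, the conditional rate is indeed 12-19%. But the SAP names no such test for IENFD; it only reports means and SDs. For the chi-square it does name, the rate is about 5-9% in that unlucky sixth of trials, so its main harm is unstable and low power.

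A reader might also credit baseline adjustment with the whole distance from the chi-square's 56-60% power to ANCOVA's 83-91%. Most of it comes from not dichotomising: a raw-change t-test already reaches 80%. Dichotomisation is a separate point.

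Finally, the figures lean on equal variances and on r. Inclusion Criteria require reduced IENFD and density cannot fall below zero, so baseline may well vary less than the final value; the gain is then smaller. This objection stands as a limit on size. It does not remove the omission.

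**Conclusion.** The point holds as one of conditional chance bias and lost precision, not as a type I error defect. The SAP measures baseline IENFD in everyone, states no balancing on it, and compares the arms without it. For correlations of 0.3-0.7, adjustment adds about 3 to 11 percentage points of power over an unadjusted comparison of mean change, and it removes a shift of 15-23% of the planned effect per SE of baseline imbalance. The planned chi-square's power differs by roughly a factor of two between favourable and unfavourable baseline luck. These sizes depend on normality, equal variances, and an SD back-solved from a sample size that the documents do not justify. The precision gain vanishes near r = 0.9. It is a worthwhile, nearly free improvement; it does not invalidate the trial.

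**What to change.** In the analysis paragraph of the SAP, analyse the primary endpoint by ANCOVA: final-visit IENFD on treatment arm, with baseline distal-leg IENFD as covariate, at the plan's one-sided 5% level. Regressing change instead of final value on the same terms gives the same treatment estimate, so the endpoint stays as defined. Report the adjusted mean difference with its confidence interval beside the raw means and SDs, and give the responder proportions as supportive.

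If the responder test stays primary, prespecify this ANCOVA as the baseline-adjusted analysis of the same endpoint, and acknowledge that the primary test itself then remains unadjusted. The text is in the past tense; if outcome data were already seen, label the ANCOVA as a later addition.

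Cost: one SAP sentence and one degree of freedom, with no new data, visits or biopsies.

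### The low screening IENFD that helps admit a patient is also the endpoint baseline, so both arms should drift upward; the planned zero placebo change ignores this, though the randomised comparison is not biased

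*Combined protocol and SAP*

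**What the plan says.** Inclusion Criteria: "Subjects also required evidence of reduced intra-epidermal nerve fiber density (IENFD) seen on skin biopsy in the region corresponding to examination abnormalities". The standard is age- and sex-matched norms; no numerical cut-off is given.

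Screening lists "skin biopsy evaluation of nerve fiber density at the distal leg and proximal thigh using standard methodology". Study Procedures then says "At the screening and final study visits all subjects also completed skin biopsies at the distal leg", and the skin biopsy section says "Follow-up biopsies were taken 21-25 weeks later on the same leg adjacent to the original biopsy sites". No second pre-treatment biopsy is described. An earlier result is expressly accepted for antibody titers, but nothing similar is said for biopsies.

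The last paragraph of the Statistical Analysis Plan says that for biopsy results "the difference between baseline (screening period) and the end of the final visit was calculated". No adjustment for baseline is specified.

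Primary Outcome states: "We anticipated no change in IENFD between visits 1 and 8 in the placebo treatment arm". The sample-size paragraph repeats it: "The sample size of 10 participants per group was determined with an assumed change in IENFD rate of 0 fibers/millimeter in the placebo group", against more than 2.0 fibers/mm on IVIG. The only data cited for the IENFD assumption come from a lifestyle study in diabetic neuropathy, in which 25% of patients gained more than 2 fibers/mm over a year. Regression to the mean is not mentioned.

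**The concern.** Patients are chosen for a low count on a noisy measurement, and that same count appears to be subtracted from the final one. Among patients selected this way, the error in the first count is negative on average and the error in the second is zero on average. The mean change is therefore positive even if no nerve regrows. Blinding to treatment does not remove this. The counting section says only "All patients underwent IENFD counting by a blinded physician and results were expressed as a linear density for IENFD", without masking to time point.

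The stake is mainly interpretation. The stated interest is disease modification, and the pilot is meant to inform a larger trial. A rise within the IVIG arm, or the share of its patients gaining more than 2.0 fibers/mm, would be partly selection and partly noise. If carried into the next design as an IVIG effect, it would be too large. The planning contrast is also affected, but only on one reading of the IVIG figure.

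**Working it through.** **1. The plan's own sample size.** Inputs from the sample-size paragraph: 0 versus 2.0 fibers/mm, one-sided 5%, 80% power, 10% dropout, 10 per group. No SD is stated, so the figure cannot be reproduced directly. Working backwards with 9 evaluable per arm, since 9/(1 − 0.10) = 10:

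SD = 2.0 / [(1.645 + 0.842) × √(2/9)] = 2.0 / 1.172 = 1.71 (1.63 using the t distribution).

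Reading it instead as 0% versus 25% responders does not give 10. That needs 21 per arm one-sided without continuity correction, or 24 with dropout. The SD of 1.71 is therefore an inference, used below as the best available anchor.

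**2. Largest error that this SD allows.** If all variation in change were measurement error, the single-biopsy error SD would be 1.71/√2 = 1.21. Any true variation in change makes it smaller.

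**3. Size of the drift, closed form.** Under normality, expected rise = (σw²/σt) × φ(c)/Φ(c). Here σw is the within-person SD, σt the total SD, and Φ(c) the share of screened patients below the cut-off. All three are assumed: σt 2–4, σw 0.6–1.2, share 20–80%.
- Smallest: (0.36/4) × 0.350 = 0.03 fibers/mm (σt 4, σw 0.6, 80% below).
- Half below: 0.07 (σt 4, σw 0.6) to 0.57 (σt 2, σw 1.2).
- Largest: (1.44/2) × 1.400 = 1.01 (σt 2, σw 1.2, 20% below).

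**4. Size of the drift, simulation.** Assumptions: true IENFD N(6, 3), N(5, 2.5) or N(4, 2), truncated at 0; entry if the first count is below 5; no true change.

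| Error SD | Mean rise, fibers/mm |
|---|---|
| 0.6 | about 0.1 |
| 1.0 | 0.25–0.34 |
| 1.21 | 0.35–0.48 |
| 1.5 | 0.53–0.70 |
| 2.0 | 0.85–1.14 |

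An error SD of 2.0 means a change SD of about 2.8. At that SD, 9 per arm has only about 42% power for a 2.0 difference before any drift, so the last row does not fit the plan's own sample size.

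**5. How many responders come from selection?** With no entry selection, P(change > 2.0) = 1 − Φ(2/(σw√2)): 8%, 17% and 24% at error SDs of 1.0, 1.5 and 2.0. With selection, the simulation gives 10–11%, 22–25% and 31–36%. Selection thus adds roughly 2–3, 5–8 and 7–12 points; the rest is ordinary noise around a cut-off.

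**6. Effect on power** (SD 1.71, 9 per arm, one-sided). If the IVIG change is 2.0 in total:

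| Placebo rise | Difference | Power | n per arm with dropout |
|---|---|---|---|
| 0 | 2.0 | 80% | 10 |
| 0.25 | 1.75 | 70% | 14 |
| 0.5 | 1.5 | 59% | 18 |
| 1.0 | 1.0 | 34% | 40 |

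If the drift is added to both arms, the difference stays 2.0, power 80% and n 10. The responder test behaves alike. Chi-square power is 54% with no drift. For rises of 0.25, 0.5 and 1.0 it becomes 47%, 39% and 24% if IVIG response is held at 50%, but 57%, 59% and 62% if both arms are lifted.

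These calculations take the responder event as an increase, as Primary Outcome defines it. The analysis paragraph counts a decrease of at least 2.0; that conflict is a separate matter and must be reconciled.

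**The case against.** The strongest objection is that the trial is randomised and blinded and its test compares arms. A reader might infer that regression to the mean biases the treatment comparison. It does not: the expected pull is the same in both arms and cannot create a difference where none exists. A reader might also infer that the trial is underpowered for this reason. That follows only if the IVIG figure is a total that already contains the drift, which the documents do not settle. Nor is a chance imbalance in qualifying counts between two groups of 10 a bias; it is random variation already reflected in the test's error rate, and adjustment improves precision. All of this stands.

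The size is also open. The documents give no repeatability figure, population mean or cut-off, and a precise count makes the drift negligible. Untreated decline over 21–25 weeks would offset it, so a net placebo rise is not established. Using one biopsy for both purposes is the natural reading but is not stated outright. Entry is judged where the examination was abnormal, non-length-dependent patients are admitted, and the thigh is also biopsied. A patient who qualified at the thigh is not selected on the distal-leg value. Imputing no change for dropouts dilutes the drift slightly.

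It is fair, too, that the plan specifies no within-arm test. But Primary Outcome sets its expectations arm by arm and defines response as an absolute gain, which invites that reading. None of these points supports a planning value of exactly zero.

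**Conclusion.** The point holds in limited form. Selection on a low screening count should pull follow-up counts upward in both arms, and the zero placebo change ignores this without placebo or repeatability data behind it. In the simulated populations the rise is about 0.1 to 1.1 fibers/mm over error SDs of 0.6 to 2.0, and about 0.35 to 0.48 at an error SD of 1.21, the most that the back-solved change SD allows. That narrower range also depends on the assumed populations and cut-off. The closed form, under its own assumptions, runs from 0.03 to 1.0, the top needing only one screened patient in five to fall below the cut-off.

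The consequence is for interpretation: within-arm rises and absolute responder rates are not dependable evidence of disease modification. Loss of power is conditional on how the IVIG figure is read. It would also be too strong to attribute most placebo responders to selection, since measurement noise alone accounts for the larger part.

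**What to change.** 1. In the analysis paragraph, add the between-arm difference in final IENFD adjusted for baseline IENFD (ANCOVA), with its confidence interval, beside the responder comparison.
2. In the sample-size paragraph, express the planning effect as a between-arm difference and state the SD used.
3. In Primary Outcome, state that within-arm rises will not be read as treatment effect, and say which biopsy and site qualify a patient and which value is the baseline.

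Cost: some wording, one extra model and one degree of freedom with about 18–20 patients. Baseline IENFD is already collected, and the precision gain is likely to be modest. If results have already been seen, the adjusted analysis should be labelled post hoc.

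Optional, if sections are retained: the existing reader recounts screening and final sections together, masked to time point, and the recount serves as baseline. This addresses counting error and reader drift but leaves skin-sampling error in place. The documents do not show how the error divides between the two, so its benefit is unknown. A specific non-zero placebo value is not proposed, because no figure in the documents supports one.

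### Sizing is on a change in IENFD (0 versus >2.0 fibers/mm) but the primary test is a chi-square on responders; without an SD or responder rates, the 80% power cannot be tied to that test

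*Combined protocol and SAP*

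**What the plan says.** The Primary Outcome paragraph defines a measured quantity: "The primary efficacy endpoint for this study was the change in IENFD between visits 1 and 8". It then sets a threshold of clinical relevance: "We defined a clinically relevant change in disease endpoint as a >2.0 fiber/millimeter increase in IENFD between screening and final visit".

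The sample-size paragraph stays on the fibers/mm scale. It reads "The sample size of 10 participants per group was determined with an assumed change in IENFD rate of 0 fibers/millimeter in the placebo group", then "and >2.0 fibers/millimeter in the IVIG group, a 1-sided α of 5%, and 80% power between the 2 groups". An allowance for one patient in ten dropping out, two in all, is built into the 10 per arm. The same paragraph says that the study, although a pilot, "was powered to answer the primary endpoint analysis".

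The closing analysis paragraph names a different comparison for the primary outcome: "the proportion of patients with a decrease of at least 2.0 fibers/millimeter was compared between the IVIG and placebo groups with a χ^2 test", followed by "with mean and standard deviations reported". No between-group test of those means is planned. Missing values count as no change, so a dropout is a non-responder. The secondary t-test is described as two-tailed; nothing is said about the sidedness of the chi-square or about a continuity correction.

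No SD of the IENFD change and no planning responder rate for either arm appears anywhere. The one percentage, 25%, comes from earlier lifestyle studies in diabetic neuropathy and supports the choice of cut-off; it is not offered as a rate for this trial.

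**The concern.** Power belongs to a particular test. A difference of 2.0 fibers/mm becomes a sample size only through an SD, whereas a chi-square on responders depends on two proportions. The plan states the effect on the first scale and tests on the second, and gives no input that connects them. Its statement that the trial was powered for its primary analysis therefore cannot be checked.

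Two consequences follow. Cutting a measured change at 2.0 discards information, which matters with 10 patients per arm. And because the sizing is one-sided while the chi-square's sidedness is open, the same data could be called positive or negative.

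**Working it through.** **Inputs from the plan.** 10 per arm; difference 2.0 fibers/mm (the lower limit of the stated >2.0); one-sided 5%; 80% power; 10% dropout, two patients in total; missing counted as no change.

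**Assumptions not in the plan.** Normally distributed changes with equal SD; IVIG mean exactly 2.0 unless stated; one dropout per arm. The event is taken as an increase, as the Primary Outcome paragraph defines it. That the analysis paragraph says decrease is a separate matter.

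**1. Can 10 per arm be reproduced?** Not from stated inputs, but two different designs reach it.

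- *Means:* n = 2·SD²·(1.645 + 0.842)²/2.0². SD 1.0 gives 4 per arm, SD 1.7 gives 9, SD 2.0 gives 13 and SD 3.0 gives 28. At SD 1.7, 9/0.9 = 10.
- *Proportions:* n = [1.645·√(2p̄(1−p̄)) + 0.842·√(p₀(1−p₀) + p₁(1−p₁))]²/(p₁−p₀)². With 50% versus 0%, p̄ = 0.25, so n = (1.007 + 0.421)²/0.25 = 8.16. That rounds up to 9, and 9/0.9 = 10. Two-sided it is 10.51, or 11.

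The same total fits either reading, and the plan supplies the inputs for neither.

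**2. If the sizing was on means, what does the chi-square deliver?** Solve the noncentral t for the SD giving 80% one-sided power at 9 per arm (16 df, noncentrality 2.0/(SD·√(2/9))): SD = 1.633. Placebo patients then cross 2.0 with probability 1 − Φ(2.0/1.633) = 0.110, and IVIG patients with probability 0.50.

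The chi-square power comes from exact binomial enumeration with 9 completers plus one imputed non-responder per arm, 10 per arm analysed, rejecting at signed z ≥ 1.645 (one-sided) or |z| ≥ 1.960 (two-sided):

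| Responders, IVIG vs placebo | Uncorrected, 1-sided / 2-sided | Continuity-corrected, 1-sided / 2-sided |
|---|---|---|
| 50% vs 11% | 57% / 38% | 38% / 21% |
| 50% vs 5% | 74% / 55% | 55% / 34% |
| 50% vs 0% | 91% / 75% | 75% / 50% |

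For 50% versus 11%, the proportions formula asks for 17 per arm one-sided or 21 two-sided, before dropout.

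**3. Same data, test of means.** Simulation under the same imputation (200,000 runs per setting), IVIG mean 2.0, one-sided power:

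| SD | Chi-square | t-test | Gap (points) |
|---|---|---|---|
| 1.0 | 83% | 99% | 16 |
| 1.5 | 62% | 85% | 23 |
| 1.63 | 57% | 79% | 22 |
| 2.0 | 45% | 64% | 19 |
| 2.5 | 34.5% | 48.5% | 14 |

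Two-sided at SD 1.63 the t-test has 67%. ANCOVA at SD 1.63 (100,000 runs) has 76%, 80% and 85% one-sided for baseline-change correlations of 0, −0.3 and −0.5.

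**4. Larger IVIG effects.** At SD 1.63 the one-sided chi-square has 76% power at an IVIG mean of 2.5 (t-test 92%) and 90% at 3.0 (t-test 98%). It reaches 80% at a mean of about 2.6 one-sided or 3.1 two-sided.

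**5. Sidedness.** For 3/10 versus 0/10 responders, p̄ = 0.15 and z = 0.3/√(0.15·0.85·2/10) = 1.879, so p = 0.030 one-sided and 0.060 two-sided.

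**The case against.** The best defence is that the trial was meant as a responder trial all along. The threshold of clinical relevance follows directly after the endpoint, it is supported by a proportion of patients, and no change is expected on placebo. The sizing sentence even speaks loosely of a rate, and 50% versus 0% gives 10 per arm. On that view the plan is under-described and not inconsistent. This is possible, and it is why the power claim is not called wrong. But the sizing is expressed in fibers/mm, the named endpoint is the change, and a responder calculation would still need two rates that the plan does not state.

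The second defence is that the 57% is built on an SD back-solved from a t-test, with the IVIG mean placed exactly at the cut-off. That is fair. Other readings give 74% to 91% one-sided, and the gap to the t-test narrows to about 16 points at a mean of 2.5 and 8 at 3.0.

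Third, not all of the gap is lost information. With both arms at 11% responders, the nominal 5% one-sided chi-square rejects only about 2.4% of the time. The t-test's two-sided 67%, which corresponds to about 2.5% in the upper tail, suggests that roughly 12 of the 22 points at SD 1.63 reflect this lower error rate. It is still power that the chosen test does not deliver at the stated alpha.

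Finally, this is a pilot reported in the past tense. That limits what can be changed, but the plan itself claims power for the primary analysis.

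**Conclusion.** The concern holds. The defined endpoint and the sizing are on the change in fibers/mm, the only primary test is on a proportion, and neither an SD nor arm-level responder rates are given. The 80% therefore cannot be shown to apply to the chi-square. This conclusion needs no assumption.

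The size of the problem does depend on assumptions. With an IVIG responder rate of 50%, one-sided uncorrected power runs from 57% to 91% as the assumed placebo rate falls from 11% to 0%; a larger IVIG mean raises it. With normal changes and an IVIG mean of 2.0, the chi-square gives up 14 to 23 points against a t-test for SDs from 1.0 to 2.5. Confidence is high in the mismatch and the missing inputs. The point should be fixed, but it does not show that the trial was underpowered.

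**What to change.** Make the primary analysis the between-group difference in mean IENFD change, by ANCOVA with baseline IENFD as covariate, at the stated one-sided 5%. Report a confidence interval; a two-sided 90% interval matches that alpha. State the SD used for sizing. Keep the comparison of patients with an increase above 2.0 fibers/mm as supportive, with an exact test.

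If the chi-square stays primary, state the planning responder rate for each arm, the sidedness and any continuity correction, and restate the power for that test at 10 per arm under the no-change imputation.

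If the data are already unblinded, label any change of primary test post hoc and still report the chi-square as planned.

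The cost is small. No new data are needed, because IENFD is already recorded in fibers/mm at both visits. ANCOVA uses one degree of freedom, so with no baseline correlation it has slightly less power than the t-test (76% against 79% one-sided). Fisher's exact test has the power of the continuity-corrected chi-square (38% instead of 57% in the 50% versus 11% case), which is acceptable only because that comparison becomes supportive. If the chi-square is kept, the stated power may have to come down.
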